### 7.3 Tables for comparison of patient and clinician data

For tables comparing patient and clinician data, the FAS dataset is used for analysis only in the instances patient data has corresponding clinician week 12 data. All data tables in this section pertain to FAS population.

**Table 7.3.1. Acne Severity Evaluation for All Patients**

Question	Baseline (N=x)		Week 4 (N=x)		Week 8 (N=x)		Week 12 (N=x)	
	A9 Patient	S9A Clinician	A9 Patient	P2 Clinician	A9 Patient	P2 Clinician	A9 Patient	P2 Clinician
Overall, how is the patient's facial acne right now?	N, Mean (SD), Median, Min, Max							
Clear (0)	n (%)							
Almost Clear (1)	n (%)							
Mild (2)	n (%)							
Moderate (3)	n (%)							
Severe (4)	n (%)							
Clear/Almost Clear	n (%)							

NOTE: All patient data corresponds to data from adult patients, pediatric patients aged 12-17, and caregivers of patients aged 9-11.

Data from Clinician and Patient DCF used; X patients had missing data; The denominator for the percentages is the number of patients with available data (N=X).

**Table 7.3.2. Acne Severity Evaluation for Adult Patients**

Question	Baseline (N=xx)		Week 4 (N=xx)		Week 8 (N=xx)		Week 12 (N=xx)	
	A9 Patient	S9A Clinician	A9 Patient	P2 Clinician	A9 Patient	P2 Clinician	A9 Patient	P2 Clinician
Overall, how is the patient's facial acne right now?	N, Mean (SD), Median, Min, Max							
Clear (0)	n (%)							
Almost Clear (1)	n (%)							
Mild (2)	n (%)							
Moderate (3)	n (%)							
Severe (4)	n (%)							
Clear/Almost Clear	n (%)							

Note: All patient data corresponds to data from adult patients,

Data from Clinician and Patient DCF used; X patients had missing data; The denominator for the percentages is the number of patients with available data (N=X).

**Table 7.3.3. Acne Severity Evaluation for Caregivers of Patients aged 9-11 yrs**

Question	Baseline (N=xx)		Week 4 (N=xx)		Week 8 (N=xx)		Week 12 (N=xx)	
	A9 Patient	S9A Clinician	A9 Patient	P2 Clinician	A9 Patient	P2 Clinician	A9 Patient	P2 Clinician
Overall, how is the patient's facial acne right now?	N, Mean (SD), Median, Min, Max							
Clear (0)	n (%)							
Almost Clear (1)	n (%)							
Mild (2)	n (%)							
Moderate (3)	n (%)							
Severe (4)	n (%)							
Clear/Almost Clear	n (%)							

NOTE: All patient data corresponds to data from caregivers of patients aged 9-11

Data from Clinician and Patient DCF used; X patients had missing data; The denominator for the percentages is the number of patients with available data (N=X).

**Table 7.3.4. Acne Severity Evaluation for Pediatric Patients Age 12-17**

Question	Baseline (N=xx)			Week 4 (N=xx)			Week 8 (N=xx)			Week 12 (N=xx)		
	A9 Patient	Q1 Caregiver	S9A Clinician	A9 Patient	Q1 Caregiver	P2 Clinician	A9 Patient	Q1 Caregiver	P2 Clinician	A9 Patient	Q1 Caregiver	P2 Clinician
Overall, how is the patient's facial acne right now?	N, Mean (SD), Median, Min, Max											
Clear (0)	n (%)											
Almost Clear (1)	n (%)											
Mild (2)	n (%)											
Moderate (3)	n (%)											
Severe (4)	n (%)											
Clear/Almost Clear	n (%)											

NOTE: All patient data corresponds to data from pediatric patients aged 12-17

Data from Clinician and Patient DCF used; X patients had missing data; The denominator for the percentages is the number of patients with available data (N=X).

**Table 7.3.5. Patient-Caregiver Comparison: Parent Understanding of Child's Acne-Related Concerns**

	Statistics		Baseline (N=x)		Week 12 (N=x)	
	Parent	Child	Parent	Child	Parent	Child
Question:	Q2: Do you feel that you understand your child's acne-related concerns right now?	AH10: Do you feel that your parents understand your acne-related concerns?	Q2: Do you feel that you understand your child's acne-related concerns right now?	AH10: Do you feel that your parents understand your acne-related concerns?	Q2: Do you feel that you understand your child's acne-related concerns right now?	AH10: Do you feel that your parents understand your acne-related concerns?
Answers:						
	N, Mean (SD), Median, Min, Max					
Not at all (0)	n (%)					
A little (1)	n (%)					
Somewhat (2)	n (%)					
Quite a bit (3)	n (%)					
Very Much (4)	n (%)					
Not at all/A little	n (%)					
Quite a bit/Very	n (%)					
Much						
Somewhat	n (%)					

Note: X patients had missing data; The denominator for the percentage is the number of patients with available data (N=X)

**Table 7.3.6. Patient-Caregiver Comparison: Parental Concerns of Child's Acne Vs. Child's Concerns**

	Statistics	Baseline (N=x)		Week 12 (N=x)	
	Parent	Child	Parent	Child	
Question:	Q3: Over the past 7 days, how concerned have you been about your child's acne?	AH4: Over the past 7 days, how worried have you been about your acne?	Q3: Over the past 7 days, how concerned have you been about your child's acne?	AH4: Over the past 7 days, how worried have you been about your acne?	
Answers:					
	N, Mean (SD) Median, Min, Max				
Not at all (0)	n (%)				
Slightly (1)	n (%)				
Somewhat (2)	n (%)				
Moderately (3)	n (%)				
Extremely (4)	n (%)				
Not at all/Slightly	n (%)				
Moderately/Extremely	n (%)				
Somewhat	n (%)				

Note: X patients had missing data; The denominator for the percentage is the number of patients with available data (N=X)

**Table 7.3.7. Patient-Caregiver Comparison: Child's Ability to Reach Future Goals**

	Statistics	Baseline (N=x)		Week 12 (N=x)	
	Parent	Child	Parent	Child	
Question:	Q4: How concerned are you about your child's ability to accomplish future goals and reach full potential due to acne?	AH9: How concerned are you that your acne will affect your ability to reach your future goals (in school or work) and be the best you can be?	Q4: How concerned are you about your child's ability to accomplish future goals and reach full potential due to acne?	AH9: How concerned are you that your acne will affect your ability to reach your future goals (in school or work) and be the best you can be?	
Answers:					
	N, Mean $\pm$ SD, Median, Range				
Not at all (0)	n (%)				
Slightly (1)	n (%)				
Somewhat (2)	n (%)				
Moderately (3)	n (%)				
Extremely (4)	n (%)				
Not at all/Slightly	n (%)				
Moderately/Extremely	n (%)				
Somewhat	n (%)				

Note: X patients had missing data; The denominator for the percentage is the number of patients with available data (N=X)

## 7.4 Tables from Clinician DCF: Safety Data Analysis

These analyses will use Safety Population dataset.

*All patients who started the study and received at least one dose of the sarecycline during the study observation period, as part of usual care. This corresponds to the entire cohort of 300 eligible patients who started the study.*

**Table 7.4.1. Safety Analysis Population**

S1: Population	Total
Adult Patient	n (%)
Pediatric Patient & Caregiver	n (%)
Total Population	n (%)

Note: Data from Patient DCF

**Table 7.4.2. PROSES Study Duration & Seysara Treatment Duration**

	Total
Cumulative study duration, n (%) a	
Day 1 (all)	300 (100%)
≥ 4 Weeks 	N (%)
≥ 8 Weeks 	N (%)
= 12 Weeks 	N (%)
Cumulative treatment duration, n (%) a	
Day 1 (all)	300 (100%)
≥ 4 Weeks 	N (%)
≥ 8 Weeks 	N (%)
= 12 Weeks 	N (%)
Treatment duration (days) b	N
	Mean (SD)
	Median
	Min, Max

N = number of subjects in the safety population; n = number of subjects within a specific Category.

aDistribution categories were cumulative; subjects were included in each category for which they qualified.

bTreatment duration is the total number of pills used across each treatment period between study encounters. Number of pills used for each encounter is calculated as a difference between 30 (maximum # of tablets in a Seysara® bottle dispensed for each study encounter) and # of unused/returned pills (by subject) at the following study encounter.

XX patients discontinued before week-4 encounter.

XX patients discontinued between week-4 and week-8 encounter.

XX patients discontinued between week-8 and week-12 encounter.

**Table 7.4.3. Seysara Treatment Compliance**

Average Compliance		
At Week 4 encounter		N, Mean % (SD) Median Min, Max
At Week 8 encounter		N, Mean % (SD) Median Min, Max
At Week 12 encounter		N, Mean % (SD) Median Min, Max

Compliance (%) for Week-4 encounter period =

$$[\# \text{ of pills expected to be used} - \# \text{ of pills unused}] * 100 / [\# \text{ of pills expected to be used}]$$

Compliance (%) for Week-4 encounter period =

$$[(AB2 - AB201) - (AA2 - AA201)] * 100 / [(AB2 - AB201)]$$

Compliance (%) for Week-8 encounter period =

$$[\# \text{ of pills expected to be used} - \# \text{ of pills unused}] * 100 / [\# \text{ of pills expected to be used}]$$

Compliance (%) for Week-8 encounter period =

$$[(R2 - R201) - (Q2 - Q201)] * 100 / [(R2 - R201)]$$

Compliance (%) for Week-12 encounter period =

$$[\# \text{ of pills expected to be used} - \# \text{ of pills unused}] * 100 / [\# \text{ of pills expected to be used}]$$

Compliance (%) for Week-12 encounter period =  
$$[(H2 - H201) - (G2 - G201)] *100 / [(H2 - H201)]$$

Note: Variables for "# of expected pills to be used" for each encounter needs to be calculated, and final Compliance % needs to be transformed, as outlined in Section 6.6.2.

**Table 7.4.4.1. Overall Summary of Adverse Events – Any Type (Subject Level)**

N=300	
[P4 or P5] Subjects with at least 1 adverse event (any type)*	n (%)
[P4_i_4 or P5_i_4]: Intensity of adverse event, among Subjects with at least 1 adverse event (any type)*	
R1: Mild	n (%)
R2: Moderate	n (%)
R3: Severe	n (%)
[P4_i_3 or [P5_i_3]: Action taken with Seysara, among Subjects with at least 1 adverse event (any type)*	
[P4_i_3r1 or P5_i_3r1]: Drug withdrawal / study discontinuation	n (%)
Other Actions	n (%)
[P4_i_5 or [P5_i_5]: Subjects with at least 1 SAE or Serious ADR	n (%)
Subjects with at least 1 SAE or Serious ADR resulting in death	n (%)

\*includes not related AEs and ADRs (related-AEs); excludes special safety events.

Note: Percentages were based on the total number of subjects in the study.

Deaths, AEs/ADRs, SAEs, and Serious ADRs were those that started on or after the date of the first dose of the study treatment and no more than 30 days after the date of the last dose of the study treatment.

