## 5 STUDY MEDICATION

The study protocol will require identification and selection of patients considered as candidates for a specific medication, namely, sarecycline (Seysara®), as part of usual care. In this context, the study medication will be sarecycline (Seysara®). Site Investigators shall provide the commercial supply of sarecycline (Seysara®) to eligible study Subjects.

Sarecycline has a restricted market access in the U.S, with payers reimbursing for the commercial prescriptions on a restricted basis. Selection of only the patients who are able to fill the prescription for reimbursed sarecycline may not be representative of individuals who might be candidates for sarecycline in the U.S; this may impact the generalization of the study results. To avoid this potential selection bias and improve the prospect of generalization of study results, the commercial supply of sarecycline (Seysara®) will be supplied to Site Investigators for the study duration of 12 weeks.

Per FDA prescribing information, the recommended dosage of sarecycline is once daily with or without food:

- 60 mg for patients who weigh 33-54 kg,
- 100 mg for patients who weigh 55-84 kg,
- 150 mg for patients who weigh 85-136 kg. approximately 1.5 mg/kg once daily

The Site Investigators will prescribe relevant sarecycline dose to patients per their clinical judgement. Correspondingly, sarecycline prescribed dose at the start of the study and any subsequent modifications to dose during the study observation period will be captured as part of study data collection.

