## 5.6 Safety Assessments

### 5.6.1 *Definition of Adverse Events & Adverse Drug Reactions*

An AE is any untoward medical occurrence in a patient administered a pharmaceutical product which does not necessarily have a causal relationship with this treatment. An AE can therefore be any unfavorable and unintended sign, symptom, or disease temporally associated with the use of a medicinal product, whether or not related to the medicinal product.

The Site Investigators used the following terms to assess the severity of each AE:

- Mild: Awareness of symptoms or signs, but easily tolerated (acceptable).
- Moderate: Enough discomfort to interfere with usual activity (disturbing).
- Severe: Interferes significantly with ability to do work or usual activity (unacceptable).

A Serious Adverse Event (SAE) is any experience that suggests a significant hazard, contraindication, side effect or precaution. With respect to human clinical experience, this includes any event which:

- results in death,
- is life-threatening,

- requires inpatient hospitalization\* or prolongation of hospitalization, unless hospitalization is for:
  - routine treatment or monitoring of the studied indication, not associated with any deterioration in condition.
  - elective or pre-planned treatment for a pre-existing condition that is unrelated to the indication under study and has not worsened since the start of study drug.
  - treatment on an emergency outpatient basis for an event not fulfilling any of the definitions of a SAE given above and not resulting in hospital admission.
  - social reasons and respite care in the absence of any deterioration in the subject's general condition.
- results in persistent of significant disability / incapacity, or
- is a congenital anomaly / birth defect,
- is a significant or important medical event that, based on appropriate medical judgment, may jeopardize the subject or may require intervention to prevent one of the other outcomes listed above.

\* Hospitalization is defined as an overnight (in-patient) stay at the hospital or emergency room.

For all AEs (either related or not related to study medication), information about the outcome (resolved or ongoing) and the action taken with the study treatment (drug withdrawn, dose reduced, dose increased, dose not changed, not applicable) were documented.

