### 6.2 Analysis Populations and Datasets

Statistical analysis and data tabulation will be performed using the following analysis populations unless specified otherwise:

- **Safety Population:** All patients who received at least one dose of sarecycline during the study observation period, as part of usual care. This in essence constitute all 300 Subjects recruited into the study.
- **Full Analysis Set (FAS):** All patients within the Safety Population that had at least one question answered pertaining to study primary research objective. This in essence will constitute all Subjects who completed their Week-12 survey. By definition, this would exclude all Subjects who were terminated (for any reason) at any timepoint (prior to Week-12) in the study.

In the event that the safety population and FAS differ, all safety evaluations (part of additional objectives) will be conducted among the safety population, while FAS will be used to conduct

analyses addressing rest of the study objectives, including the description of population demographics, primary and secondary objectives, and select additional (non-safety related) objectives.

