## 7.2 Tables from clinician's DCF (FAS Population)

Clinician data is analyzed using the FAS dataset. In relevant instances (such as IGA and physician satisfaction evaluations), only FAS dataset with corresponding week 12 clinician data is used. All data tables in this section correspond to FAS population.

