**Table 7.2.5. Seysara Treatment Characteristics**

Character	Baseline (N=x)	Week 4 (N=x)	Week 8 (N=x)	Week 12 (N=x)
Prescription dose	(M12.1)	(P13A1)	(P13A1)	(P13A1)
60 mg	n (%)	n (%)	n (%)	n (%)
100 mg	n (%)	n (%)	n (%)	n (%)
150 mg	n (%)	n (%)	n (%)	n (%)
Prescription frequency	(M12.2)	(P14A1)	(P14A1)	(P14A1)
Once daily	n (%)	n (%)	n (%)	n (%)
Other 1	n (%)	n (%)	n (%)	n (%)
Other 2	n (%)	n (%)	n (%)	n (%)

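### No planned summary specifies a count of dose reductions or increases: the AE overviews leave them in an undefined residual row, and the one dose table gives net visit totals among Week-12 completers

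*SAP*

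**What the plan says.** **Collected.** SAP 5.6.1, like Protocol 8.6.1, lists the actions documented for every AE, related or not: "drug withdrawn, dose reduced, dose increased, dose not changed, not applicable". Protocol 8.6.2 asks investigators to indicate whether events led to stopping or to a dose change. Dose changes are also collected whether or not an AE is involved. Protocol Section 5 states that "any subsequent modifications to dose during the study observation period will be captured", and Protocol 7.3 to 7.5 ask for modifications at Weeks 4, 8 and 12.

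**Reported, AE tables.** Tables 7.4.4.1, .2, .4, .6, .7 and .10 have two action rows, one for drug withdrawal or study discontinuation and one labelled "Other Actions". The second label is not defined. Tables 7.4.4.3, .5, .8 and .11, by organ class and preferred term, have an action column filled with placeholder letters and no n (%). Tables 7.4.4.9 and 7.4.4.12 list the action for each event by patient. SAP 6.8 plans counts of discontinuations and mentions no dose-change count.

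**Reported, dose.** Table 7.2.5 gives n (%) for 60, 100 and 150 mg, with a separate block for "Prescription frequency", at Baseline and Weeks 4, 8 and 12. It has no row for change or direction of change. For its population, SAP 7.2 states: "All data tables in this section correspond to FAS population". SAP 6.2 says of the FAS: "By definition, this would exclude all Subjects who were terminated (for any reason) at any timepoint (prior to Week-12) in the study".

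**The concern.** Safety and tolerability of sarecycline is a stated objective. The plan takes the trouble to record whether each AE led to a lower dose, a higher dose or no change, and then specifies no number for the first two. In the overview tables, an ADR followed by a dose reduction and one that needed no change would fall in the same row.

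The dose table does not fill the gap, for two reasons. It shows how many subjects were on each strength at a visit, and not how many moved. It also leaves out the subjects who stopped early, although SAP 6.2 assigns safety evaluations to the Safety Population. A dose change that was not tied to an AE, in a subject who later left the study, would appear in no planned table or listing.

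**Working it through.** The plan states no figure on this point, so there is none to reproduce. The check compares what is collected with what each shell can show, and then runs two illustrations on assumed numbers.

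**1. Where a dose reduction or increase could appear**

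| Output | Population | What it shows |
|---|---|---|
| Six overviews (7.4.4.1, .2, .4, .6, .7, .10) | Safety | Withdrawal counted; the rest in one residual row |
| Preferred-term tables (7.4.4.3, .5, .8, .11) | Safety | Action column with placeholders, no n (%) |
| By-patient listings (7.4.4.9, .12) | Safety | Action for each event; AE-linked only; no totals |
| Table 7.2.5 | FAS | Subjects per strength and per frequency at each visit |
| Table 7.4.2 | Safety | Duration from tablets used (30 minus returned, summed over periods) |
| Table 7.4.3 | Safety | Compliance from tablets expected and unused |

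In Tables 7.4.2 and 7.4.3 a 60, 100 or 150 mg tablet each counts as one, so neither can show strength. No row of this inventory specifies a number of subjects or events with dose reduced or dose increased.

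**2. The residual row**

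Five categories are collected and one is broken out: 5 − 1 = 4 categories are left for the residual row, unless some are dropped. On either reading, reductions and increases have no count of their own.

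Assumed example: 60 subjects with one AE each, 6 of them withdrawn.
- Profile A: 0 reduced, 0 increased, 54 unchanged. Residual row = 0 + 0 + 54 = 54.
- Profile B: 15 reduced, 3 increased, 36 unchanged. Residual row = 15 + 3 + 36 = 54.

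The two profiles print identically.

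**3. Net totals in Table 7.2.5**

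Assumed example: 271 completers, of whom 8 go from 100 to 60 mg and 8 go from 60 to 100 mg, with everyone else unchanged (68 on 60 mg, 135 on 100 mg, 52 on 150 mg).
- Baseline: 68 + 8 = 76 on 60 mg; 135 + 8 = 143 on 100 mg; 52 on 150 mg.
- Week 12: 76, 143 and 52 again.

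Sixteen subjects changed strength and the table shows no difference.

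More generally, suppose the totals are the same at both visits and more than half of the N subjects are on one strength, with r_max subjects on it. The number of changers compatible with the table then runs from 0 to 2 × (N − r_max). With an assumed 25/55/20% split:
- FAS 240 (60/132/48): up to 2 × (240 − 132) = 216.
- FAS 270 (68/148/54): up to 2 × (270 − 148) = 244.
- FAS 300 (75/165/60): up to 2 × (300 − 165) = 270.

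These are arithmetic limits and not expected values. They show that visit totals carry almost no information on how many subjects changed.

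**4. Who is missing from Table 7.2.5**

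The SAP puts the Safety Population at 300 and expects attrition without giving a rate. For assumed FAS sizes of 240 to 300, the table omits 300 − 240 = 60 down to 300 − 300 = 0 subjects, at every encounter including Baseline.

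**The case against.** The strongest reply is that the detail is already in the planned output. The pooling is confined to the overview tables. The preferred-term tables carry an action column, and the two listings give the action for every event, with dates, by patient. An ADR followed by a reduction and one followed by nothing are separate entries there, and AE-linked changes could be tallied by hand. A reader might infer that dose changes are never reported, or that nobody could tell how many patients had one. For AE-linked changes the documents do not support that, and this part of the reply stands. What is missing is a specified count, and any summary at all of changes not linked to an AE beyond the net visit totals.

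A reader might also infer that exposure is described only in completers. That is too broad: Tables 7.4.2 and 7.4.3 give treatment duration and compliance in the Safety Population. Only strength and frequency are confined to the FAS.

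Three further points are fair. The content of the residual row is inferred by exclusion, because the SAP does not define it. The placeholder cells do not rule out counts; they leave the matter open. And the plan breaks no promise: Protocol 12.6.6 and SAP 6.8 commit to AE frequencies and discontinuations, and neither names dose change as a tolerability measure. These points lower the weight of the concern. They do not supply the missing count.

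**Conclusion.** The point holds as a minor gap in safety reporting. No planned summary specifies how many subjects or events had a dose reduction or increase. AE-linked changes can be identified only in uncounted columns and listings. Other changes are visible only as net totals among subjects who reached the Week-12 survey, and those made before early termination are not visible at all.

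In terms of shells, six overview tables and one dose table are affected. In terms of patients, the size cannot be stated, because the documents give no dose-change or attrition figures; every patient count in the working is assumed. The conclusion rests on two readings: that the undefined row is the remainder of the five recorded actions, and that the preferred-term action cells will not hold counts, as their shells show none. The primary and secondary endpoints are untouched, and nothing here bears on whether any dose decision is appropriate.

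**What to change.** 1. In Tables 7.4.4.1, .2, .4, .6, .7 and .10, replace the residual row with counted rows for dose reduced, dose increased, dose not changed and not applicable.
2. In the subject-level tables (7.4.4.1, .2 and .4), add a footnote that a subject counts once in each category in which he or she has at least one event, so that rows may overlap and need not add up to the number of subjects with an AE.
3. Run Table 7.2.5 in the Safety Population as well as in the FAS.
4. Add within-patient rows to Table 7.2.5, from Baseline to each encounter: strength increased, strength decreased, frequency changed, sarecycline stopped, unchanged.

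The cost is edits to seven table shells (six overviews and one dose table), one repeat run and one derived within-patient change variable. The actions and dose modifications are already collected in the eDCF, so no new data are needed. Fixing the rows in the shells before the final analysis also avoids choosing afterwards which dose changes to report.
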